2 ANALYSIS POPULATIONS

The following populations for analyses are defined.

Table 3 - Populations for analyses

Population	Description
Screened	All participants who signed the ICF.
Randomized	All participants from screened population who have been allocated to a randomized intervention by IRT regardless of whether the intervention was received or not.
Intent-to-treat (ITT)	All randomized participants. Participants will be analyzed according to the intervention allocated by randomization.
Safety	All randomized participants who have taken at least 1 dose of study intervention, regardless of the amount of treatment administered. Participants will be analyzed according to the intervention they actually received.
Pharmacokinetic (PK)	All participants from the safety population with at least one post-baseline PK result. Participants having received only placebo will not be part of the PK population. Participants will be analyzed according to the intervention they actually received.
ADA	All participants from the safety population with at least one post-baseline ADA result (positive, negative or inconclusive). Participants will be analyzed according to the intervention they actually received.

Participants exposed to study intervention before or without being randomized will not be considered randomized and will not be included in any analysis population. The safety experience of these participants will be reported separately.

Randomized participants for whom it is unclear whether they took the study intervention will be considered as exposed and will be included in the safety population as randomized.

For participants receiving more than one study intervention during the study, the intervention group for as-treated analyses will be the dupilumab group.

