 - s At indicated time points serum dupilumab concentration and ADA samples will be collected and archived prior to administration of investigational product. Blood samples for PK and ADA assessment may be collected in case a suspected SAE. In response to AEs of special interest like anaphylaxis or hypersensitivity additional ADA samples may be collected at or near the event based on the medical judgment of the Investigator and/or Sponsor representative. Pharmacokinetic and ADA samples will be collected unless restricted due to local regulation. However, the PK and ADA samples will be collected for safety assessment in the event of an SAE. Samples for ADA will only be collected for analysis in the event of any SAE for participants from China sites.
 - t For sites that cannot send fungal specific IgE to central lab to test timely, additional local [REDACTED] tests or skin test may be needed to meet participant's eligibility.

x For participants ≥ 15 kg to <30 kg at screening and injection every 4 weeks, Visit 3 will be at Week 4. Parent/legally authorized representative, or caregiver injection training will be performed at this visit.

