9.3 POPULATIONS FOR ANALYSES

The following populations are defined ([Table 6](#)):

Table 6 - Populations for analyses

Population	Description
Screened	All participants who sign the ICF/assent form
Randomized	The randomized population includes all participants with a treatment kit number allocated and recorded in the IRT database, and regardless of whether the treatment kit was used or not. Participants treated without being randomized will not be considered randomized and will not be included in any efficacy population.
Intent-to-treat (ITT)	All randomized participants analyzed according to the treatment group allocated by randomization regardless if treatment kit is used or not.
Safety	All participants randomly assigned to study intervention and who take at least 1 dose of study intervention. Participants will be analyzed according to the intervention they actually received. Randomized participants for whom it is unclear whether they took the study medication will be included in the safety population as randomized. For participants who accidentally receive different treatment from the planned, the actual intervention allocation for as-treated analysis will be the dupilumab group.

Population	Description
Pharmacokinetic (PK)	The PK population includes all participants in the safety population with at least 1 non-missing result for functional dupilumab concentration in serum after first dose of the study treatment. Participants will be analyzed according to the intervention actually received.
Anti-drug antibody (ADA)	ADA population includes all participants in the safety population who have at least 1 non-missing result in the ADA assay after the first dose of the study treatment. Participants will be analyzed according to the intervention actually received.

ADA: antidrug antibody; ICF: informed consent form; IRT: interactive response technology; ITT: intent-to-treat; PK: pharmacokinetic

Endpoints not required for children aged ≥ 6 to < 12 years will be analyzed using the ITT population in adults and adolescents (≥ 12 to < 18 years).

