3.7.1.2 Immunogenicity analyses

Dupilumab anti-drug antibody (ADA) status (negative or titer value, if positive in the ADA assay) at Visit 2 (Day 1), Week 12, Week 24, Week 52 and follow up at Week 64 will be provided. The neutralizing antibody results for ADA positive samples will be provided. ADA negative samples will be imputed as NAb negative.

On-treatment ADA incidence (measurements during the treatment epoch) will be provided for the following ADA response categories. Treatment-emergent and treatment-boosted response will be defined based on samples collected in the on-treatment period.

Pre-existing immunoreactivity is defined as:

An ADA positive response in the assay at baseline with all post first dose ADA results negative, OR an ADA positive response at baseline with all post first dose ADA responses less than 4-fold over baseline titer levels.

Treatment-emergent ADA responses are defined as:

A positive response in the ADA assay post first dose, when baseline results are negative or missing.

Treatment-emergent ADA responses are further classified as persistent, indeterminate or transient

- Persistent response - defined as a treatment-emergent ADA response with two or more consecutive ADA positive sampling time points, separated by greater than ($>$) 12-week period (84 days), with no ADA negative samples in between
- Indeterminate response - defined as a treatment-emergent response with only the last collected sample positive in the ADA assay
- Transient response - defined as a treatment-emergent response that is not considered persistent OR indeterminate

Treatment-boosted response is defined as:

An ADA positive response in the assay post first dose that is greater-than or equal to 4-fold over baseline titer levels, when baseline results are positive.

Titer values (Titer value category)

- Low (Titer <1000)
- Moderate ($1,000 \leq \text{Titer} \leq 10,000$)
- High (Titer $>10,000$)

The following summary will be provided based on ADA population:

- Number (%) of participants with pre-existing immunoreactivity
- Number (%) of participants with treatment-emergent ADA
- The summary statistics (including number, median, Q1, Q3, minimum and maximum) of the peak post-baseline titer for participants with treatment-emergent ADA, and participants with persistent, indeterminate and transient ADA response
- Number (%) of participant with transient treatment-emergent ADA
- Number (%) of participants with persistent treatment-emergent ADA

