3.7.1.2.1 Association of Immunogenicity with Exposure, Safety and Efficacy

The safety and efficacy analysis mentioned below will be conducted using the following categories:

- ADA positive participants: Participants with treatment-emergent or treatment-boosted response.
- ADA negative participants: Participants with pre-existing immunoreactivity or negative in the ADA assay at all time points.

Impact of ADA on PK profile

Potential associations between ADA variables (eg, ADA peak titers, neutralizing antibody status, treatment-emergent, persistent, indeterminate and transient response, treatment-boosted) and serum concentration profile of dupilumab may be explored. Plot of serum concentration of functional dupilumab versus visit will be provided by ADA variables for the dupilumab dose group. Individual participant plots of dupilumab concentration according to ADA status will be provided to assess the impact of ADA on PK.

[figure not shown]
Impact of ADA on clinical efficacy endpoints

Associations between the ADA variables (eg, ADA peak titers, neutralizing antibody status, treatment-emergent, persistent, treatment-boosted) and the primary efficacy endpoint may be explored for the dupilumab dosed group.

Association of ADA with clinical safety endpoints

Association of safety versus ADA status may be analyzed in the ADA population. The safety assessment may focus on the following events:

- Severe injection site reactions last longer than 24 hours or serious injection site reactions
- Hypersensitivity reactions (SMQ (20000214) hypersensitivity narrow search confirmed by medical review)
- Anaphylactic reactions (SMQ (20000021) anaphylactic reaction narrow search)

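### China-site participants enter the ADA population only if they have an SAE, so the treatment-emergent ADA incidence contains an event-selected component that the SAP neither excludes nor flags

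*SAP*

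**What the plan says.** **Sampling.** Protocol Section 1.3 schedules ADA samples at Day 1 and Weeks 12, 24, 52 and 64. Footnote s gives the general rule, "Pharmacokinetic and ADA samples will be collected unless restricted due to local regulation", adds that samples are still taken for safety assessment if an SAE occurs, and then says of China: "Samples for ADA will only be collected for analysis in the event of any SAE for participants from China sites". China is one of the Asia-region countries in SAP Table 2.

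**Population.** SAP Section 2, Table 3, takes "All participants from the safety population with at least one post-baseline ADA result (positive, negative or inconclusive". Protocol Section 9.3, Table 6, has the same rule: "ADA population includes all participants in the safety population who have at least 1 non-missing result in the ADA assay after the first dose". Neither asks for a baseline sample or a scheduled sample.

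**Use.** SAP Section 3.7.1.2 introduces the ADA incidence counts with "The following summary will be provided based on ADA population". It defines a treatment-emergent response as "A positive response in the ADA assay post first dose, when baseline results are negative or missing", and limits it in time: "Treatment-emergent and treatment-boosted response will be defined based on samples collected in the on-treatment period". SAP Section 3.7.1.2.1 adds: "Association of safety versus ADA status may be analyzed in the ADA population". There, pre-existing immunoreactivity counts as ADA negative and a treatment-emergent response as ADA positive.

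**Unscheduled samples.** SAP Section 5.4 uses scheduled and unscheduled measurements alike if they fall in an analysis window. The ADA windows in Table 10 cover all time after the first dose.

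**The concern.** Everywhere else, a participant belongs to the ADA population because a visit took place. In China, a participant belongs because something serious happened. An incidence calculated over both groups mixes routine sampling with event-triggered sampling and describes neither.

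A second problem may follow from the first. A participant sampled only at an SAE may have no baseline result. Any antibody present before treatment would then be read as treatment-emergent, and in the ADA-safety comparison the participant would move from the negative to the positive group.

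Treatment-emergent ADA incidence is a listed secondary endpoint, and the protocol names systemic hypersensitivity as an important identified risk. With about 31 participants per arm, one misplaced participant is visible in the reported percentage.

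**Working it through.** The documents give no ADA rate, SAE rate or China enrolment, so there is no planned figure to reproduce. The check traces participants through the rules and then sizes the effect on stated assumptions.

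**Step 1: trace the rules.**

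| Participant | In ADA population? | Can count as treatment-emergent? |
|---|---|---|
| Non-China, routine sampling | Yes, whether or not an SAE occurs | Yes, against a Day 1 result |
| China, no SAE | No, no ADA result | No |
| China, SAE sample on treatment | Yes | Yes if positive; automatically so if baseline is missing |
| China, SAE sample after the on-treatment period | Yes, in the denominator | Not from that sample |

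The SAE rate among China members of the ADA population is therefore 100% by construction. No SAP text excludes them, flags them or plans a sensitivity analysis. The same could happen in any other country where local regulation blocks routine sampling; the documents name none.

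**Step 2: effect of one added participant.** Assume c = 4 or 8 of the 31 dupilumab participants are from China. Then m = 31 − c = 27 or 23 have routine data. With k routine positives, one added positive changes incidence by (k+1)/(m+1) − k/m.

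| k | m = 27 | m = 23 |
|---|---|---|
| 0 | 0 to 1/28 = +3.6 points | 0 to 1/24 = +4.2 points |
| 1 | 1/27 = 3.7% to 2/28 = 7.1%, +3.4 | 1/23 = 4.3% to 2/24 = 8.3%, +4.0 |
| 2 | 2/27 = 7.4% to 3/28 = 10.7%, +3.3 | 2/23 = 8.7% to 3/24 = 12.5%, +3.8 |

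An added negative does little: with k = 2 and m = 23, 8.7% becomes 2/24 = 8.3%.

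**Step 3: how many such participants to expect.** Assume a China share of 10% to 40% and an SAE risk s of 3% to 10%, the same at all sites, with every SAE yielding a post-dose sample.
- Expected entrants on dupilumab = 31 × share × s: from 31 × 0.10 × 0.03 = 0.09 to 31 × 0.40 × 0.10 = 1.24.
- P(at least one) = 1 − (1 − s)^(31 × share): from 1 − 0.97^3.1 = 9% to 1 − 0.90^12.4 = 73%.

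**Step 4: expected effect of selection alone.** Let a₀ and a₁ be ADA positivity without and with an SAE.
- True incidence = a₀(1 − s) + a₁s.
- Observed incidence = (n_other × true + n_China × s × a₁) / (n_other + n_China × s).

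Over the Step 3 ranges:
- a₀ = a₁ = 5%: no bias.
- a₀ = 5%, a₁ = 20%: 0.05 to 0.8 points upward. At the top end, (18.6 × 0.065 + 1.24 × 0.20)/(18.6 + 1.24) = 7.3% against a true 6.5%.
- a₀ = 5%, a₁ = 50%: 0.15 to 2.5 points upward.

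The SAE share in the ADA population also rises. At s = 3% it becomes 3.3% to 4.9%; at s = 10%, 11.0% to 15.6%. Misread baselines would add to the incidence figures; they are not modelled here.

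**The case against.** **The missing baseline is an inference.** Footnote s opens by saying that samples at the indicated time points are collected and archived before dosing. The China sentence may mean that samples are stored and assayed only after an SAE, so a Day 1 result could exist. This stands, and the baseline argument is therefore conditional. Selection into the population remains on either reading.

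**A false ADA-safety link does not follow.** A reader might infer that the plan is biased toward linking ADA with hypersensitivity. The documents do not support that.
- Entry from China depends on any SAE, not on ADA status, and the outcomes in SAP Section 3.7.1.2.1 (injection site reactions, hypersensitivity, anaphylaxis) are narrower than that trigger.
- An SAE-triggered negative puts an event in the ADA-negative group, which works against a link.
- A China participant sampled once has fewer chances of a positive than one sampled at four post-baseline visits.
- Extra samples near an event at other sites are at the discretion of the investigator or sponsor.

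**The consequence is limited.** The ADA-safety analysis is optional, safety analyses are descriptive, and ADA incidence is outside the testing hierarchy in SAP Section 3.5. This also stands. The incidence will still be reported as a secondary endpoint, on a denominator that the SAP does not describe correctly for China.

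**Scheduled-only ADA status would lose information.** At routinely sampled sites it would label a participant ADA negative when the only positive came at the event itself. The fix avoids this.

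**Conclusion.** The concern holds for the population definition. As written, SAE-selected China participants go into the denominator of a secondary endpoint. If no Day 1 sample was taken or assayed, any on-treatment positive among them counts as treatment-emergent.

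The likely number is 0 to 1 participant per arm. One added positive would move dupilumab incidence by about 3 to 4 points, assuming 4 to 8 China participants in that arm and 0 to 2 routine positives. The expected bias is smaller: zero if ADA is unrelated to SAEs and no baseline is misread, and at most 2.5 points from selection alone over the assumed ranges.

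Two stronger claims are not established: that China participants certainly lack a Day 1 sample, and that the ADA-safety comparison is biased in a known direction. The primary endpoint and type I error control are untouched.

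**What to change.** In SAP Table 3, require for the ADA population at least one post-baseline result from a sample collected at a protocol-scheduled ADA visit (Week 12, 24, 52 or 64 in the Schedule of Activities) and assayed whether or not an event occurred. Both conditions are needed:
- A date inside a Table 10 window is not enough, because those windows would also capture event-triggered samples.
- If China samples are archived and assayed only after an SAE, the visit condition alone would readmit the same participants.

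Leave participants whose only results are event-triggered out of the incidence and the ADA-safety summaries. Show them in a separate listing and flag positives with a missing baseline.

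For participants under scheduled sampling, keep event-time results in ADA status. A sensitivity summary using scheduled samples only is optional.

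Since Protocol Table 6 has the broader rule, record the change in the SAP's table of modifications. The cost is two sentences and one listing. The downside is that a few event-time results appear only in that listing.

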3 STATISTICAL ANALYSES

3.1 GENERAL CONSIDERATIONS

All comparisons will be of dupilumab (300 mg q2w for adults and adolescents/children ≥ 60 kg at screening, or 200 mg q2w for adolescents/children ≥ 30 kg and < 60 kg at screening, or 300 mg q4w for adolescents/children ≥ 15 kg and < 30 kg at screening) versus placebo.

A multiplicity-controlled hierarchical approach is proposed to control the overall type-I error rate for testing the primary and selected secondary efficacy endpoints at an alpha of 0.05. The study is considered positive when the primary endpoint achieves statistical significance with 2-sided significance level 0.05.

In general, continuous data will be summarized using the number of observations available, mean, standard deviation (SD), median, Q1, Q3, minimum, and maximum. Categorical data will be summarized using the count and percentage of participants.

The baseline value is generally defined as the last available value before the first dose of double-blind investigational medicinal product (IMP). For participants randomized but not treated, the baseline value is defined as the last available value before randomization.

For endpoints collected on the daily Nasal Symptom Diary, if there are 4 or more measurements collected within 7 days prior to the first dose of double-blind IMP (or prior to randomization for participants randomized but not treated), baseline is defined as the average of the scores in the 7 days prior to the first dose of double-blind IMP (or prior to randomization for participants randomized but not treated); if less than 4 measurements are collected, the baseline will be the average of the most recent 4 measurements prior to the first dose of double-blind IMP (or prior to randomization for participants randomized but not treated).

Stratification factors used in analyses will be derived based on eCRF data (for age, time from last surgery and country) and central-reading nasal endoscopy data (for disease pattern).

Unless otherwise specified, analyses will be performed by intervention group and overall for baseline and demographics characteristics.

Observation period

The observation period will be divided into 4 segments:

- The **pre-treatment period** is defined as the period up to first investigational medicinal product (IMP) administration.
- The **treatment-emergent (TE) period** is defined as the period from the first IMP administration to the last IMP administration +98 days. The treatment-emergent period includes the following 2 periods:

- The **on-treatment period** is defined as the period from the first IMP administration to the last administration of the IMP +14 days for adults and adolescents/children ≥ 30 kg at screening or 28 days for adolescents/children ≥ 15 kg and < 30 kg at screening.
- The **residual treatment period** is defined as the period from the end of the on-treatment period to the end of the treatment-emergent period.
- The **post-treatment period** is defined as the period from the end of the treatment-emergent period.

3.2 PRIMARY ENDPOINT(S) ANALYSIS

The primary endpoint detailed in this section is the change from baseline in sinus opacifications assessed by computerized tomography (CT) scans using the Lund Mackay (LMK) score at Week 52.

3.2.1 Definition of endpoint(s)

The primary endpoint is the change from baseline in LMK score at Week 52.

Lund Mackay total score is based on assessment of the CT scan findings for each sinus area (maxillary, anterior ethmoid, posterior ethmoid, sphenoid, and frontal sinus on each side). The extent of mucosal opacification is rated on a 3-point scale ranging from 0 = normal to 2 = total opacification. In addition, the ostiomeatal complex is graded as 0 = not occluded, or 2 = occluded. The maximum score is therefore 12 per side for a maximum total score of 24, corresponding to the sum of all sinuses and the ostiomeatal unit.

3.2.2 Main analytical approach

The primary endpoint will be analyzed with the estimand defined according to the following attributes:

- Endpoint: Change from baseline in LMK score at Week 52
- Treatment condition: dupilumab will be compared to placebo
- Analysis population: ITT population
- Intercurrent events (IE):
 - The following intercurrent events will be handled with a composite strategy; data after the IE will be excluded and the worst post-baseline value on or before the start of the IE will be assigned to the Week 52 value (WOCF); for participants with no post-baseline values, the baseline value will be used.
 - Undergo/plan to undergo surgery for AFRS prior to Week 52
 - Taking SCS for any reason prior to Week 52

- The following IEs will be handled with the treatment policy strategy (without IEs that need to be handled with composite strategy). All assessments after starting such IE will be included.
 - Discontinuing the study intervention
 - Taking antifungals or other prohibited/rescue medications
- Population-level summary:

The primary endpoint will be analyzed using an analysis of covariance (ANCOVA) model with the baseline LMK score, intervention group, time from last surgery (≤ 2 years, >2 years), and region (Americas: Argentina, USA, Canada; Asia: China, Japan, India, Turkey, Saudi Arabia) as covariates, with intercurrent event strategies and missing data handling as defined in [Table 3](#).

Data of participants who undergo/plan to undergo surgery for AFRS or take SCS for any reason on or before Week 52 will be excluded from analysis after the IE, and the worst postbaseline value on or before the start of IE will be used to assign missing endpoint value (for participants whose postbaseline values are all missing, the baseline will be used to impute). Participants who discontinue the intervention prematurely are encouraged to follow the planned clinical visits and in those participants who did not have any of the above IE, all data collected after intervention discontinuation will be used in the analysis. For these participants, missing data may still happen despite all efforts to collect the data after treatment discontinuation. A multiple imputation (MI) approach will be used to impute missing endpoint value, and this MI method will use all participants excluding participants with the above IE. The imputation number will be 40.

Each of the imputed complete data will be analyzed by fitting an ANCOVA model as described above. Statistical inference obtained from all imputed data will be combined using Rubin's rule. Descriptive statistics including number of participants, mean, standard error, and least squares (LS) mean changes (and standard error) will be provided. In addition, difference of the dupilumab group against placebo in LS means and the corresponding 95% confidence intervals (CI) will be provided along with the p-value.

A separate summary of primary endpoint will be provided for pediatric patients.

The multiple imputation and analysis model for the primary analysis of change from baseline in LMK values will be built with the following sample SAS code.

1. 40 datasets with a monotone missing pattern will be obtained, induced by Markov Chain Monte Carlo (MCMC) method on all participants excluding participants who undergo/plan to undergo surgery for AFRS or take SCS for any reason on or before Week 52.

```
proc mi data=ads out=monotone n impute=40 seed=16724;
  where wocfl='N';
  var time region trt01p value0 value24 value52;
  mcmc chain=multiple impute=monotone;
run;
```

2. For each of the imputed datasets with monotone missing pattern in step 1, the remaining missing data at baseline and post-baseline visits will be imputed using regression method for the monotone missing pattern with adjustment for covariates including time from last surgery (≤ 2 years, > 2 years), region (Americas, Asia) and intervention group.

```
proc mi data=monotone out=dat_mi nimpute=1 seed=16724 minimum=... 0 0 0  
maximum=... 24 24 24; /*LMK score range is 0-24*/
```

```
    by _imputation_;  
    class time region trt01p;  
    var time region trt01p value0 value24 value52;  
    monotone reg (/details);  
run;
```

3. Each of the 40 imputed datasets will be merged with one dataset imputed by WOCF approach, and then be analyzed using the main statistical model. These 40 imputed datasets will be saved.

```
%macro w1;  
    %do i=1%to 40;  
        data wocf&i.;  
        set ads;  
        where wocffl='Y';  
        _imputation_=&i.;  
        run;  
    %end;  
    data wocf_all;  
        set %do j=1 %to 40; wocf&j. %end;;  
        run;  
    %mend w1;  
  
%w1;  
  
data mi;  
    set dat_mi wocf_all;  
run;  
  
proc sort data=mi; by _imputation_; run;  
  
proc glm data=mi;  
    by _imputation_;  
    class time region trt01p;  
    model change=time region trt01p value0;  
    lsmeans trt01p / stderr;  
    estimate 'Diff dupilumab vs placebo' trt01p -1 1;  
    ods output LSMeans=lsmeans Estimates=estimates;  
run;
```

4. Applying Rubin's rules to combine analysis results (point estimates and standard errors) from 40 imputations using PROC MIANALYZE for the LS means and difference in LS means between dupilumab and placebo.

```
proc sort data=lsmeans; by trt01p _imputation_; run;  
  
proc mianalyze data=lsmeans;  
    by trt01p;  
    modeleffects lsmean;  
    stderr stderr;  
    ods output ParameterEstimates=lsmean;  
run;  
  
proc mianalyze data=estimates;  
    modeleffects estimate;  
    stderr stderr;  
    ods output ParameterEstimates=lsmeandiff;  
run;
```

